Statistical analysis plan for Inpatient versus Outpatient Care after Anterior Cervical Decompression and Fusion: A prospective randomised non-inferiority trial

NCT03979443

August 16th 2022

We, the Blinded Data Interpretation Committee of the FACADE trial, have reached a consensus on how to carry out the blinded data interpretation (BDI). The document coined "Minutes for FACADE blinded data interpretation" (next page) outlines the execution of the blinded data interpretation for the FACADE trial.

Statistical analysis will be carried out by the trial statistician without any involvement from members of the Blinded Data Interpretation Committee or other FACADE investigators, as outlined below. The central study coordinator will code the trial data (two treatment arms) as 'Group A' and 'Group B' before handing the data over to the statistician. This will help ensure that the statistical analyses will be performed blind to the treatment allocation.

To reduce risk of interpretation bias, blinded results from the ITT analysis (Group A vs. Group B) will be presented to the Blinded Data Interpretation Committee. The Blinded Data Interpretation Committee will then contemplate on two alternative written interpretations, one where group A is the Inpatient care strategy and one where Group A is the Outpatient care strategy. Only after the Blinded Data Interpretation Committee has reached a consensus on the proper interpretation of the findings, the central study coordinator will unblind the treatment group allocation.

Also, as Drs. [name] and [name] were involved in the clinical care of the patients, they will recuse themselves from making any interpretations but are to take part in the blinded data interpretation meeting to answer potential questions regarding the execution of the trial.

Finally, the undersigned (members of the FACADE Blinded Data Interpretation Committee) agree that the minutes of the upcoming blinded data interpretation meeting will be emailed to an independent scientist for external review (comments/requests for clarification) before the final manuscript is submitted.

FACADE Blinded Data Interpretation Committee

August 16, 2022

[name], PhD (Chair, co-PI of the FACADE)

[name]
[name], PhD (Co-Chair)

[name], Trial statistician

[name], PhD (FACADE PI)

Minutes of the FACADE Blinded Data Interpretation meeting for Manuscript:

The full study protocol of the FACADE study has been published¹. The participating centers and study group are listed in the Supplementary Appendix. The trial was designed and conducted by the FACADE investigators and the analyses were completed at the coordinating center. The trial protocol was approved by ethical review at the institutional review board of the Helsinki and Uusimaa Hospital District on June 6, 2019 (1540/2019) and duly registered at ClinicalTrials.gov (NCT03979443: <https://clinicaltrials.gov/ct2/show/NCT03979443>). All participants provided written informed consent. The trial was monitored by Clinical Research Unit of the Helsinki University Hospital (HYKSIN Institute), Helsinki, Finland. The writing committee of the FACADE trial vouch for the accuracy and completeness of the data, the fidelity of the trial to the protocol, and the complete reporting of adverse events. There was no industry involvement in the trial.

The FACADE trial was launched in the coordinating center (Helsinki) on June 12, 2019. The next trial center (Turku University Hospital) joined the trial on January 16, 2020 and the third (Oulu University Hospital) on January 23, 2020. Both Helsinki and Turku retained in the trial until patient recruitment was completed (February 12, 2021). However, due to Covid-19 situation, Oulu was able participate trial only until May 30, 2020.

Participants

During the recruitment period of the trial, we screened all patients suffering from radiating arm pain referred to the study centers for trial eligibility (n=782). After being fully informed of the trial protocol, 104 eligible patients willing to participate (written informed consent) were randomized.

Randomization and Blinding

After the surgery, all patients were taken to the recovery room for 2 to 3 hours for an immediate postoperative observation. When we had confirmed that the patients were fully conscious and co-operative, and immediate postoperative complications were

ruled out using a postoperative checklist, patients' final eligibility was confirmed. A member of the FACADE study group then randomized the patients either to the Outpatient group (discharge within the same day) or the Inpatient group (overnight surveillance at the hospital). The randomisation was a built-in property in the online electronic case report form (eCRF) system used in the trial (Granitics Ltd., Espoo, Finland). To minimise the risk of predicting the treatment assignment of the next eligible patient (to ensure concealment), we performed randomisation with variable block size (block size known only to the statistician with no involvement in the clinical care of the participants in the trial).

Study Interventions

Outpatient group

A ward nurse evaluated all patients allocated to the Outpatient group approximately 6-8 hours after surgery using a standardised FACADE discharge checklist. If the patient fulfilled all discharge criteria, he/she was instructed on how to deal with any concerns and was discharged. At discharge, we documented the time elapsed from operation and provided the patients with prescriptions to manage postoperative pain and an absence from work medical certificate for the first postoperative week.

Inpatient group

Patients allocated to inpatient care were kept in the hospital for surveillance overnight. A neurosurgeon on duty assessed whether patients were fit to be discharged on the 1st postoperative day. Identically to the Outpatient group, we documented the time elapsed from operation at discharge. We also provided the patients with prescriptions for postoperative pain management and an absence from work medical certificate for the first postoperative week.

Outcome measures

Primary (efficacy) outcome measure

Our primary outcome measure was the Neck Disability Index (NDI; scale 0 to 100, with higher scores indicating worse outcomes and more symptoms), a validated, neck-specific, patient reported measure of pain-related dysfunction^{2,3}. We used a validated Finnish version of the NDI⁴. The primary assessment time point was six months. We also gathered the NDI at one and three months postoperatively, but this data was only intended to illustrate the trajectory of the treatment responses (Table 2). Our pre-defined threshold for minimal important difference (MID) of the primary outcome (NDI) was set at 17.3% (improvement from the baseline value), based on previous literature⁵.

Details of all other outcome measures can be found in the protocol and the Supplementary Appendix.

Sample size

Originally, the trial was powered to detect an MID in the NDI score between the two study groups. We set the MID for NDI (17.3%) as our margin of non-inferiority Δ based on the results by Parker et al.⁵ Assuming no difference between treatment arms ($\epsilon = 0$ in NDI score improvements), equal sample sizes ($x=1$, the SD 23%), a margin of non-inferiority Δ of 17.3%, one-sided 2.5% statistical significance criteria ($z_\alpha = 1.96$) and 90% statistical power ($z_\beta = 1.28$), the required sample size was 44 patients per study

group. When also taking a dropout rate of 15% into account, the group size increased to 52 patients. Accordingly, we set the recruitment target at 104 patients.

However, while our statistician (TC) was preparing the plan for blinded data interpretation, he noticed that we had erroneously chosen an incorrect value for SD (in the study by Parker et al.⁵, the mean improvement for NDI was 23.2 while the standard deviation (SD) was 19.7%). Keeping all other parameters constant, he recalculated the required sample size: The recruitment target turned out 29 subjects per group (without adjusting for dropouts) and 35 subjects per group (after adjusting for a 15% dropout rate), respectively.

Statistical analysis

The trial is primarily designed to ascertain whether outpatient care is non-inferior to inpatient care, at 6 months after surgery, with NDI as the primary outcome. Only one primary analysis will be used to assess non-inferiority. At the 6-month time point, non-inferiority can be claimed if the lower limit of the CI (based on difference in means in the NDI) is greater than the MID in the primary comparison.

According to the CONSORT (Consolidated Standards of Reporting Trials) statement for non-inferiority and equivalence trials⁶, secondary outcomes can be managed using either a superiority or equivalence framework. In our trial, all secondary outcomes will be assessed with an equivalence hypothesis, but since our trial is not necessarily powered for these comparisons, and to avoid issues with multiplicity, we consider them exploratory or hypothesis-generating.

We will follow primarily intention-to-treat (ITT) principle in all our analyses. In the ITT analyses, the participants are included as randomised. Per-protocol and on-treatment analyses will also be used to avoid falsely claiming non-inferiority. Summary statistics will be given as mean (with SD) for continuous variables and as frequencies (with %) for categorical variables. Repeated measures mixed model (RMMM) analysis will be used for all continuous variables (both primary and secondary outcomes) where regression coefficients are allowed to differ between study subjects. Statistical significance is set to two-sided 5% level. The RMMM analysis allows the use of all available observations in the data set, so the full data set (data set without multiple imputation) will be used in the analysis. Logistic regression will be used to assess categorical variables. STATA (Statistics/Data analysis, SE v15.1, StataCorp LLC, 4905 Lakeway Drive, College Station, Texas 77845 USA) will be used for analyses.

Blinded data interpretation

The data will be interpreted according to a blinded data interpretation scheme we have published and described in detail previously.[5] In brief, FACADE statistician (TC) will carry out the statistical analyses, blinded to the group assignment, and presents the data as Group A and Group B. The FACADE Blinded Data Interpretation committee will then contemplate on the blinded results until a consensus on the interpretation is reached. Once the Blinded Data Interpretation committee reaches a consensus, the data will be unblinded and no changes are made to the interpretation of the results.

In keeping with the pre-defined interpretation plan for the FACADE trial, we will adhere to the following plan in presenting and interpreting the data (presented as Group A and Group B to preserve blinding) at the BDI meeting:

1. Analysis on efficacy (primary, non-inferiority analysis): Is outpatient care non-inferior to inpatient care after anterior cervical decompression and fusion?

- Table 1. Baseline characteristics.
- Table 2. Primary outcome (NDI) at the primary outcome assessment time point (6 mo).
- Figures 2 and 3: Two possible scenarios – Group A vs. Group B and Group B vs. Group A.

Based on this data, we will make an initial (blinded) interpretation on non-inferiority.

2. Treatment-related adverse consequences of both treatment strategies (Safety concerns)

Before finalising our interpretation on clinical relevance of our findings, we will assess the safety of the two treatment arms:

Table 3. Complications, adverse events, re-admissions to hospital

According to our own data on the safety of the ACDF procedure (overall complications rates < 10%), this analysis will likely not be powered to materially change our main conclusion, particularly with regards to the most feared complication (neck haematoma), which has a reported incidence of <1%.

Having said this, to be completely transparent and inclusive about the possible effect of adverse consequences on the clinical relevance (our interpretation) of the trial findings, we commit to assessing the overall rate (incidence) of safety concerns before final interpretation is made as follows:

If we detect > 10% difference in the overall incidence of serious adverse events between the two group (treatment strategies), we will add the following notion in our conclusion:

“However, there was a noteworthy imbalance in the incidence of safety concerns in the two treatment strategies (higher/lower rate in Group A) and this should be considered when interpreting the trial findings.”

As noted, the analysis on the downsides of the two treatments will not change our assessment on efficacy, rather modify our interpretation on the clinical relevance of the trial.

The sequence of events to take place in the upcoming “blinded data interpretation meeting” is outlined in the flow chart below:

1. Analysis on efficacy (primary, non-inferiority): Is outpatient care non-inferior to inpatient care after anterior cervical decompression and fusion?

Table 1. Baseline characteristics.

Table 2. Primary outcome (NDI) at the primary outcome assessment time point (6 months).

Figure 2. Scenario 1: Group A minus Group B.

Figure 3. Scenario 2: Group B minus Group A.

Initial interpretation on efficacy

2. Incidence of safety concerns: Imbalance?

Table 3. Complications, adverse events, re-admissions to hospital (with 30 days post-operatively), and reoperations.

NO

Initial interpretation on efficacy stands

YES

A notion on downsides to be added to the initial interpretation on efficacy

3. Unblinding

4. Unblinded interpretation on efficacy and clinical relevance

5. Final interpretation (signed by all involved)

1. Analysis on efficacy (primary, non-inferiority): Is outpatient care non-inferior to inpatient care after anterior cervical decompression and fusion?

[figure not shown]
Table 1. Baseline characteristics.

	Group A	Group B
	Mean ± SD	Mean ± SD
Age (years), mean (SD)		
Gender (female), n		
Dominant hand affected, n		
Work Ability Score (WAS)		
Physically demanding job: "heavy labor", n		
Patient's own estimate of job demands: "heavy" n		
Ability to work normally irrespective of the symptoms? n		
Participation in leisure time activities irrespective of the symptoms? n		
Duration of symptoms (days), mean (SD)		
Preoperative sick leave (days)		
Prior treatments (Physiotherapy) n		
NSAID Pain medication, n		
Opioid pain medication, n		
Neuropathic pain medication, n		
Neck Disability Index (NDI) (scale: 0 to 100), mean (SD)		
Neck pain at rest (NRS scale: 0 to 10), mean (SD)		
Arm pain at rest (NRS scale: 0 to 10), mean (SD)		
EuroQol-5 dimensions-5 levels Time Trade-Off index score (0 to 1)		
EuroQol-5 dimensions-5 levels Health Visual Analogue Scale (0 to 100)		

Table 2. Primary outcome at the primary outcome assessment time point (6 months).

Table 2. Primary outcome at six months		Group A	Group B	Difference (95% CI)
		Mean \pm SE	Mean \pm SE	
Primary efficacy outcome				
Neck Disability Index (Scale: 0 to 100)		?? \pm ??	?? \pm ??	?? \pm ??
*Means and standard errors are derived from a general linear repeated measures model analysis.				
Abbreviations: CI: Confidence Interval; SE: Standard Error				

Our judgment on the efficacy (non-inferiority) will be based on the location of the whole CI in relation to Δ (non-inferiority margin), as outlined by Piaggio et al⁶.

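### The non-inferiority margin is defined as a 17.3% improvement from baseline but tested against a between-group difference in mean NDI, and its value in NDI points is never stated

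*SAP*

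**What the plan says.** Under "Outcome measures" the primary outcome is the NDI, "scale 0 to 100, with higher scores indicating worse outcomes and more symptoms". The same paragraph gives the only definition of the minimal important difference (MID): it "was set at 17.3% (improvement from the baseline value"), a figure taken from earlier published work.

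Under "Sample size" the MID becomes the margin: "We set the MID for NDI (17.3%) as our margin of non-inferiority". The true difference is taken as zero "in NDI score improvements), equal sample sizes", and the SD is given as 23%, later corrected to 19.7%. The sentence making that correction gives the mean improvement as 23.2 with no unit and its SD with a percent sign.

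Under "Statistical analysis" the criterion for non-inferiority is met "if the lower limit of the CI (based on difference in means in the NDI) is greater than the MID in the primary comparison". Table 2, both in its blinded form and in the unblinding section, reports the outcome as "Neck Disability Index (Scale: 0 to 100") with a between-group difference and its 95% CI. The text on interpreting the confidence interval refers only to Δ, without a number or unit.

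**The concern.** The description of the MID is of a change from a baseline value. The quantity tested is a difference between two group means at six months, in score units. One number cannot serve as both unless the text says how to get from one to the other, and it does not.

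The SAP allows one primary analysis of non-inferiority, and the verdict depends on where the confidence interval lies relative to Δ. The committee will have the baseline table, including mean baseline NDI, and the Table 2 interval in front of it when it decides. If the unit of Δ is still open then, it could be settled with the interval already known, which blinded interpretation is meant to prevent.

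**Working it through.** **Inputs from the SAP.** Margin 17.3%; SD 23%, then 19.7%; one-sided 2.5% (z = 1.96); 90% power (z = 1.28); true difference 0; 1:1 allocation; 44 per group, 52 with 15% dropout; after correction of the SD, 29 and 35.

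**Assumption.** The SAP gives no mean baseline NDI. A range of 30 to 60 is used.

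**1. The plan's own figures.** n per group = 2 × [SD × (1.96 + 1.28) / Δ]².
- SD 19.7, Δ 17.3: 2 × (19.7 × 3.24 / 17.3)² = 27.2, so 28 (29 with a t-based calculation). The stated 29 is reproduced.
- SD 23, Δ 17.3: 2 × (23 × 3.24 / 17.3)² = 37.1, so 38 (39 with t). The stated 44 is not reproduced; that is a separate matter.
- Dropout: 44 / 0.85 = 51.8, so 52; 29 / 0.85 = 34.1, so 35. Both agree.

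The formula uses only the ratio of SD to margin. It therefore requires the two to share a scale, but does not say which scale. What points to NDI points is the combination with Table 2 and the decision rule: both use a difference in mean NDI on the 0 to 100 scale, and no planned table or model uses percent change.

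**2. The margin if the definition is applied literally as a percentage of baseline.** Δ = 0.173 × mean baseline.

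| Assumed mean baseline | Δ in points |
|---|---|
| 30 | 5.2 |
| 40 | 6.9 |
| 50 | 8.7 |
| 60 | 10.4 |

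This equals 17.3 points only if the mean baseline is 100, the top of the scale.

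**3. Can the reading change the verdict?** The half-width of an unadjusted 95% CI is 1.96 × SD × √(2/n).
- SD 19.7: 1.96 × 19.7 × √(2/44) = 8.2 points with 44 per group; 7.6 with 52.
- SD 23: 9.6 and 8.8 points.

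Take an observed difference of zero, 44 per group and SD 19.7. The interval is −8.2 to 8.2. Against 17.3 points, outpatient care is non-inferior. Against 6.9 points (assumed baseline 40), the interval contains both zero and Δ, which the SAP's scheme calls inconclusive. The relative margin exceeds the half-width only when the mean baseline is above 8.23 / 0.173, about 48 (about 56 with SD 23: 9.61 / 0.173).

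**4. What kind of disagreement is it?** With 44 per group and SD 19.7 the full interval is about 16.5 points wide. If its upper limit is below 17.3, its lower limit is below about 0.8, which is under every margin in the table. At that width, an interval that is non-inferior against 17.3 points could be inconclusive against the smaller margin, but it could not lie wholly above it.

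**The case against.** The best defence is that 17.3% on a 0 to 100 scale simply means 17.3 points. The baseline phrase can be read as a 17.3-point change from baseline, and the SAP uses the percent sign loosely elsewhere, as in the sentence on the mean improvement and its SD. The sample-size section, Table 2 and the plot against Δ all suit points. The example graphs are not available in the text reviewed and may label the axis. Most of this stands: points is the likelier intention. It does not rescue the wording, because the sentence describing a change from baseline is the only definition of the MID, and even in points a change from baseline is not a between-group difference.

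A reader might go further and infer that the trial is badly underpowered. Power of 23% to 77% does result for baselines of 30 to 60, SD 19.7 and 44 to 52 per group, against 98% to 99% at 17.3 points. The documents do not support that inference. The low figures take the margin as a percentage of an assumed baseline while keeping the SD in points, and the SAP never combines them that way. If margin and SD are both points, or both percent change, the ratio 17.3 / 19.7 and the power are unchanged.

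Nor do the documents show that the statistician would apply the wrong number, or that the two readings give non-inferior against inferior. The contrast is non-inferior against inconclusive.

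**Conclusion.** The point holds as a mismatch between the definition of the margin and the quantity tested, with the unit left unstated in the visible text. The evidence within the SAP favours 17.3 NDI points, so the definition should be brought into line with the test.

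The size of the problem is the gap between the two readings: about 5 to 10 points against 17.3. An unfavourable confidence limit within that gap would change the verdict. At an assumed baseline of 40 even an observed difference of zero would be affected. This rests on the assumed baselines, on SDs taken as NDI points, and on unadjusted intervals; the planned mixed model could narrow them.

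It is worth settling before results are seen because it concerns the trial's only decision threshold.

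**What to change.** Before the committee sees the results, state the margin once and use it identically in the primary outcome section, the statistical analysis section and the text accompanying the non-inferiority figure: Δ = 17.3 NDI points on the 0 to 100 scale, applied to the outpatient-minus-inpatient difference in mean NDI at 6 months. Remove the phrase about improvement from baseline as the definition of the margin.

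If the pre-defined margin was in fact relative, the SAP should say so, analyse the outcome on that same scale and restate the power. The margin should not be derived from the trial's own baseline data, since recruitment has ended and that would make a pre-defined threshold depend on the data.

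The direction of the rule is a separate defect: it asks for a lower limit greater than the MID although higher NDI is worse. It should be reconciled with the figure text in the same revision.

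For a margin in points the cost is wording only. A relative margin would also need a change to the analysis and a new power statement.

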Based on the location of the whole CI in relation to Δ (non-inferiority margin), our initial interpretation on the non-inferiority of Outpatient care (vs. Inpatient care), is as follows:

Scenario 1 (Figure 2) [incorrect options to be removed]

Group A is [superior **A** / non-inferior **B** to **D** / inferior **H**] to Group B after anterior cervical decompression and fusion.

OR

Our results are inconclusive [**E** to **G**] regarding the non-inferiority of the two groups after anterior cervical decompression and fusion.

Scenario 2 (Figure 3) [incorrect options to be removed]

Group B is [superior **A** / non-inferior **B** to **D** / inferior **H**] to Group A after anterior cervical decompression and fusion.

OR

Our results are inconclusive [**E** to **G**] regarding the non-inferiority of the two groups after anterior cervical decompression and fusion.

2. Safety concerns

Table 3. Complications, adverse events, re-admissions to hospital (with 30 days post-operatively), and reoperations.

	Group A	Group B
Acute perioperative complications	n	n
Serious Adverse Events (SAE)	Below % will represent % of SAE/MAE/Cause of reop in group A not % of total N	Below % will represent % of SAE in group B not % of total N
Cardiovascular event	n (%)	n (%)
Pulmonary embolus	n (%)	n (%)
Deep venous thrombosis in leg	n (%)	n (%)
Subcutaneus neck haematoma	n (%)	n (%)
Systemic infection	n (%)	n (%)
Postoperative hemi- or tetraplegia	n (%)	n (%)
Persistent dysphonia at 6 months	n (%)	n (%)
Persistent dysphagia at 6 months	n (%)	n (%)
Death	n (%)	n (%)
Other	n (%)	n (%)
Minor Adverse Events (MAE)		
Wound infection	n (%)	n (%)
Motor deficit (new)	n (%)	n (%)
Persistent symptoms	n (%)	n (%)
Dyspnea (return to hospital)	n (%)	n (%)
Re-admissions to hospital (< 30 days)	n (%)	n (%)
Cause of reoperation		
Impaction of implant	n (%)	n (%)
Dislocation of implant	n (%)	n (%)
Foraminal re-stenosis	n (%)	n (%)
Wound infection	n (%)	n (%)
Wound opening	n (%)	n (%)
Other cause	n (%)	n (%)

Imbalance between the two groups in the crude incidence of safety concerns?

YES / NO

- If NO, our initial interpretation on efficacy (previous page) stands as is.
- If YES => We will add the following notion about the imbalance (excess in harms) to our interpretation:

“However, there was a noteworthy imbalance in the incidence of safety concerns in the two treatment strategies (higher/lower rate in Group A) and this should be considered when interpreting the trial findings.”

3. Unblinding

After consideration of the major downsides of the two treatment groups, we have now reached a consensus on our blinded assessment on efficacy.

Our statistician will now unblind the treatment group assignment (break the randomization code):

Group A = Inpatient care / Outpatient care [incorrect option to be removed]

Group B = Inpatient care / Outpatient care [incorrect option to be removed]

Given the above noted, the FACADE data is shown in **Table 1** (with n-values for Groups to be added) and in Scenario 1 (**Figure 2**) or Scenario 2 (**Figure 3**). [incorrect option to be removed]

Table 2. Primary outcome at the primary outcome assessment time point (6 months).

	Group A	Group B	Difference (95% CI)
	Mean \pm SE	Mean \pm SE	
Primary efficacy outcome			
Neck Disability Index (Scale: 0 to 100)	?? \pm ??	?? \pm ??	?? \pm ??
*Means and standard errors are derived from a general linear repeated measures model analysis.			
Abbreviations: CI: Confidence Interval; SE: Standard Error			

Figure 2 or Figure 3

4. Unblinded interpretation on efficacy and clinical relevance

Accordingly, our interpretation of the FACADE trial is as follows:

[incorrect options to be removed]

(1) Inpatient care is superior to outpatient care after anterior cervical decompression and fusion. However, be it noted that we did not set a superiority hypothesis in the study protocol.

OR

(2) Inpatient care is non-inferior to outpatient care after anterior cervical decompression and fusion.

OR

(3) Inpatient care is inferior to outpatient care after anterior cervical decompression and fusion.

OR

(4) Our results are inconclusive regarding the non-inferiority of the two groups after anterior cervical decompression and fusion.

In addition to the primary conclusion above, the following notion regarding downsides of the two treatments will / will not be added [incorrect option to be removed] based on our assessment of the need for safety concerns (Section 2):

“However, there was a noteworthy imbalance in the safety of the two treatment strategies (higher/lower [incorrect option to be removed] rate in Outpatient care) and this should be considered when interpreting the trial findings.”

5. Final interpretation

Our final interpretation of the FACADE trial stands as follows:

[Copy & paste the correct interpretation]

Place: ZOOM-/Teams-meeting
Time: [Insert date here]

[name]

[name]

[name], trial statistician

Also present at the meeting (as external observers):

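### Two Table 3 rows, dyspnoea and readmission, cannot be scored by an inpatient during the first night, and the perioperative row is not anchored to randomisation

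*SAP*

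**What the plan says.** The SAP's Randomization and Blinding section gives the order of events. After surgery, "all patients were taken to the recovery room for 2 to 3 hours for an immediate postoperative observation". Immediate postoperative complications were then "ruled out using a postoperative checklist, patients' final eligibility was confirmed", and only after that were patients randomised.

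Under Study Interventions, outpatients were assessed for discharge at about 6 to 8 hours after surgery. For the other arm, "Patients allocated to inpatient care were kept in the hospital for surveillance overnight", with fitness for discharge judged on the first postoperative day. The time of discharge was recorded in both arms.

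Three rows of Table 3 (section 2, Safety concerns) matter here:

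- "Acute perioperative complications", a count with no start, end or definition, placed above the serious adverse events.
- "Dyspnea (return to hospital)", listed among the minor adverse events.
- Readmission within 30 days, which the caption counts from the operation.

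The SAP words the use of this table in two ways. The text on blinded interpretation adds a caveat to the conclusion if overall serious adverse events differ by more than 10%. The flow chart that follows refers to Table 3 as a whole, and the form under Safety concerns asks for a yes or no on "Imbalance between the two groups in the crude incidence of safety concerns", with no threshold.

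**The concern.** The two strategies differ mainly in where the patient spends the first night. A safety row that is to be compared between arms should therefore mean the same thing in both arms during those hours. A row defined by coming back to hospital does not, because a patient who has not left cannot come back. A difference in these rows would partly reflect the definition and not the care.

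The perioperative row raises a different question. Anything that happened in theatre or the recovery room came before allocation and cannot have been caused by it, yet the row stands in the table on which imbalance between the strategies is judged.

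What is at stake is the safety caveat attached to the trial's conclusion. The SAP states that the safety review leaves the efficacy assessment unchanged.

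**Working it through.** **Timeline, from the SAP**

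| Time | Outpatient arm | Inpatient arm |
|---|---|---|
| 0 to 2-3 h after surgery | recovery room, checklist | recovery room, checklist |
| about 2-3 h | randomised | randomised |
| about 6-8 h | discharge assessment | in hospital |
| first night | at home, if discharged | in hospital |
| day 1 | at home | discharge assessment |

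**Same event, same hour.** Take a patient who becomes breathless during the first night.

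- Discharged outpatient who comes back: can score on the dyspnoea row and on the readmission row.
- Inpatient: can score on neither. No other row names in-hospital dyspnoea. It could be recorded only in a row without a definition (the perioperative row or the serious-event row for other events), or through a serious cause that has its own row.

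The asymmetry lasts from outpatient discharge to inpatient discharge. After that, both rows mean the same in both arms.

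**Size.** The SAP gives no overnight return rate, so the rate r is an assumption. Inputs from the SAP: 104 patients randomised 1:1, that is 52 per arm if exactly balanced, and an overall complication rate below 10%. Suppose every affected outpatient returns and no inpatient event is recorded elsewhere. The expected outpatient count is then 52 × r, against 0 in the inpatient arm. This is an upper bound for any given r.

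As a yardstick only, the last column gives the chance that these rows alone differ by more than 10 points. That needs at least 6 patients, since 5/52 = 9.6% and 6/52 = 11.5%. The chance is P(X ≥ 6) with X binomial (52, r).

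| r (assumed) | 52 × r | P(X ≥ 6) |
|---|---|---|
| 2% | 1.0 | 0.06% |
| 4% | 2.1 | 1.7% |
| 6% | 3.1 | 9.0% |
| 10% | 5.2 | 42% |

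The last line is an extreme, because the SAP expects complications of all kinds to stay below 10%.

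**Perioperative row.** Events before allocation have the same expected rate in both arms, so they bring no directional bias, only noise and dilution. Illustration with an assumed post-randomisation contrast of 5% against 0%, to which an independent 5% of earlier events is added in both arms:

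- Outpatient: 1 − 0.95 × 0.95 = 9.75%. Inpatient: 5%.
- Difference: 4.75 points, against 5 before.
- Rate ratio: 9.75/5 = 1.95; before, the inpatient rate was zero.
- Exact two-binomial chance of a difference above 10 points in either direction: 12.6%, against 4.5% before.

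With no true difference, that chance is 1.4% at a common rate of 5% and 7.1% at 10%.

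**Which rule the rows reach.** Dyspnoea is a minor event, readmission lies outside the serious-event rows, and the perioperative row stands above that heading. On the table's layout none of the three feeds the trigger of more than 10% in serious events. All three can feed the judgement in the flow chart and the form, which refer to Table 3 or to safety concerns in general.

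**The case against.** Several objections have force.

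- **Most of Table 3 does not depend on location.** Cardiovascular events, pulmonary embolus, haematoma, infection, paralysis, death and the causes of reoperation carry no return condition. A reader might infer that the whole table uses the wrong risk window. The SAP does not support that; the problem lies in the rows named.
- **The content of the perioperative row is not stated.** A reader might infer that it counts events from before randomisation. The SAP does not say so. Immediate complications were ruled out before entry, and the row may equally hold events from the first hours after allocation. What stands is that it has no time anchor.
- **Definitions are left to the protocol.** The SAP refers to the protocol and an appendix for its other outcome measures, so a bare row label is not in itself a fault. This answers the perioperative row in part. It does not answer the dyspnoea row, where the condition of return is written into the label.
- **The rule with a number uses serious events only.** Correct, and it limits the consequence to the looser wording elsewhere in the SAP.
- **Coming back to hospital is a real consequence of early discharge.** It is, and readmission deserves to be reported. It is a post-discharge measure, however, and not a like-for-like count of harm over the first night.
- **Failed same-day discharge is a matter of adherence.** That is fair. Discharge times are recorded, and per-protocol and on-treatment analyses are planned, so its absence from a complications table does not hide it. A separate line would still help the reader.

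**Conclusion.** The point holds for two rows and, more weakly, for a third. By their stated definitions, dyspnoea and readmission cannot be scored by an inpatient during the first night, while a discharged outpatient can score on both. The direction is against outpatient care. The perioperative row is unanchored and may add noise, without favouring either arm.

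The size is modest and rests on an assumed return rate: about 1 to 3 patients of 52 at 2% to 6%, with full return and no inpatient event recorded elsewhere. A reader might infer that this artefact would by itself set off the caveat. The SAP does not support that: the 10% rule is confined to serious events, and even used as a yardstick it would be crossed by these rows in at most 9% of trials at those rates. The consequence runs through the yes/no judgement on safety concerns, which has no threshold and which a few one-sided events could sway. The efficacy conclusion is not affected.

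**What to change.** Before the blinded meeting:

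1. Count Table 3 events from randomisation, over the same period in both arms.
2. Split the perioperative row at randomisation. Show earlier events descriptively and leave them out of the imbalance judgement. Moving the whole row out of the table would risk losing harms that arose after allocation.
3. Tabulate dyspnoea wherever it occurs, with return to hospital as a sub-row.
4. Keep readmission, labelled as a post-discharge measure.
5. Report failed same-day discharge separately, from the recorded discharge times.
6. State which rows feed the imbalance judgement, and reconcile the serious-event trigger with the wider wording in the flow chart and the form.

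The cost is re-tabulation and some chart look-up for events during the inpatient stay; no new visits are needed. One asymmetry remains: inpatients are observed more closely overnight, so milder episodes may be noticed in them and missed at home. A note beside the table should say so.
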